3.1.2.2 Definition of Dose-Limiting Toxicity

With exceptions discussed below, a DLT is defined as a grade ≥3 adverse drug reaction (ADR), according to the National Cancer Institute (NCI) Common Terminology Criteria for Adverse Events (CTCAE) Version 5, occurring in the DLT evaluation period (i.e., 28 days after the initial administration of AGEN1884) in subjects enrolled in the phase 1 dose escalation.

The SRC recognizes that in the absence of prior human experience with AGEN1884, a conservative approach should be adopted in ascribing the relevance of the treatment-related toxicity to drug. Treatment-emergent serious adverse events (SAEs) will be ascribed as related to drug except in cases in which a clear relationship to the underlying disease or recognized comorbidities are evident. For this trial, the MTD is defined as the highest dose at which <2 of 6 subjects experience a DLT.

A DLT is specifically defined as any one of the following:

- Grade ≥ 2 uveitis, eye pain, or blurred vision that does not respond to topical therapy.
- Any grade ≥3 toxicity that is possibly, probably, or definitely related to AGEN1884
 occurring during the DLT evaluation period (28 days after initial administration of
 AGEN1884), except for any of the following:
 - Grade 3 infusion-related reaction resolving within 6 hours of dosing and controlled with medical management.
 - Transient (≤6 hours) grade 3 flu-like symptoms or fever, which are controlled with medical management.
 - Transient (≤24 hours) grade 3 fatigue, local reactions, headache, nausea, or emesis that resolves to grade ≤1.
 - Grade 3 diarrhea, skin toxicity, or liver function test (LFT), (alanine aminotransferase [ALT], aspartate aminotransferase [AST], or gamma glutamyltransferase [GGT]) increase that resolves to grade ≤1 within 7 days after medical management (e.g., immunosuppressant treatment) has been initiated.
 - Single laboratory values out of normal range that are unlikely related to trial treatment according to the investigator, do not have any clinical correlate, and resolve to grade ≤1 within 7 days with adequate medical management.
 - Tumor flare phenomenon, defined as local pain, irritation, or rash localized at sites of known or suspected tumor.

Subjects who do not complete the DLT observation period and do not receive 2 doses of AGEN1884 during the DLT observation period for reasons other than a DLT will be replaced.

3.1.2.3 Stopping Rules in Phase 1 for Enrollment Based on Toxicities

• If 2 or more DLTs occur at Dose Level 1 (0.1 mg/kg), then study enrollment will stop and evaluation of biologic and clinical activity will be completed for Dose Level 1. If there is a rationale to proceed at or near Dose Level 1 based on clinical or biological activity from

Confidential Page 27 of 78

enrolled subjects, then Agenus will redesign the study with new dose levels and potentially a new dose frequency, both of which would be intended to decrease the dose intensity on study, and approach the Food and Drug Administration (FDA) for guidance before activating such a redesigned study.

• The SRC will meet to review the dose cohort under evaluation as well as safety of the full cohort under evaluation. Should ≥2 subjects on any dose level experience toxicities that meet DLT criteria but occur after the DLT evaluation period, enrollment will be held and the occurrences would be thoroughly evaluated by the SRC. Should these events be consistent with DLTs, for instance, from immune-related toxicities, they will be evaluated for relatedness to AGEN1884. The SRC will evaluate the events and de-escalate the dose level due to immune-related adverse events meeting DLT criteria that occur beyond the DLT evaluation period.

3.2 Eligibility Criteria

3.2.1 Inclusion Criteria

Subjects must meet all of the following criteria:

- 1. Written informed consent.
- 2. \geq 18 years of age.
- 3. Histological or cytological diagnosis of solid cancer or lymphoma that is considered incurable and without therapies with established benefit. Biopsy is not necessary for subjects with known prior diagnosis, and clinical or radiographic evidence of recurrence.

For Phase 2 only: Subjects PD-1/PD-L1 naïve and those who experienced documented disease progression during treatment with an approved or investigational PD-1/PD-L1 inhibitor as their most recent therapy (2-6 weeks prior to first dose of study drug).

For subjects in Phase 2 with HCC: This cohort includes subjects with histological diagnoses of HCC (not including atypical histology such as cholangiocarcinoma mix or fibrolamellar hepatocellular carcinoma) who experienced documented disease progression during treatment with an approved or investigational PD-1/PD-L1 inhibitor as their most recent therapy (2-6 weeks prior to first dose of study drug).

- 4. Eastern Cooperative Oncology Group (ECOG) score of 0 or 1 (Appendix C).
- 5. Subjects in Phase 2 with HCC should have a Child-Pugh score of A or B7 with no encephalopathy or ascites (Appendix F).
- 6. Life expectancy ≥ 12 weeks.
- 7. Adequate cardiac function (New York Heart Association [NYHA] class ≤II) (Appendix D).
- 8. Adequate organ function, defined as absolute neutrophil count (ANC) $\geq 1,500 \times 10^6$ /L, absolute lymphocyte count ≥ 500 /mm³, hemoglobin ≥ 8.0 g/dL, and platelet count

Confidential Page 28 of 78

≥100,000×10⁶/mm³ without blood growth factors or without transfusions within 1 week of first dose.

For subjects in Phase 2 with HCC: Platelet count $\geq 60 \times 10^6 / \text{mm}^3$ and ANC $\geq 1,000 \times 10^6 / \text{L}$ are acceptable provided that the principal investigator assesses these abnormalities as due to liver disease.

- 9. Adequate liver function, defined as AST and ALT ≤2.5× institutional upper limit of normal (ULN), and bilirubin ≤1.5 ULN.
 - For subjects in Phase 2 with HCC: AST and ALT \leq 5 × ULN, bilirubin \leq 2 × ULN, and albumin \geq 2.8 mg/dL.
- 10. Adequate renal function, defined as estimated creatinine clearance ≥50 mL/min according to Cockcroft-Gault formula, or measured 24-hour creatinine clearance (or local institutional standard method).
- 11. Adequate coagulation defined by international normalized ratio (INR) or prothrombin time (PT) \leq 1.5 x ULN (unless the patient is receiving anticoagulant therapy); and activated partial thromboplastin time (aPTT) \leq 1.5 x ULN (unless the subject is receiving anticoagulant therapy). Subjects in Phase 2 with HCC can have an INR \leq 2.3 x ULN.
 - **Note**: Subjects in Phase 2 with HCC and on anticoagulant treatment would have an assigned value of 1 point when scoring PT/INR so the overall Child-Pugh score is not adversely affected.
- 12. Female subjects of childbearing potential and fertile male subjects must agree to use adequate contraception or abstain from sexual activity from the time of consent through 90 days after the end of study drug. Adequate contraception includes condoms with contraceptive foam; oral, implantable, or injectable contraceptives; contraceptive patch; intrauterine device; diaphragm with spermicidal gel; or a sexual partner who is surgically sterilized or postmenopausal. **Note:** Abstinence is acceptable if this is the established and preferred contraception for the subject.
- 13. In the expansion phase (Phase 2), all subjects must provide a sufficient and adequate formalin-fixed paraffin embedded (FFPE) tumor tissue sample preferably collected after progression on the last therapy and/or collected at screening, if clinically feasible. If a recent biopsy is not available, an archival FFPE sample should be provided from a site not previously irradiated. If no tumor tissue is available, a fresh biopsy will be required if clinically feasible (See Section 5.6.1 for details).

3.2.2 Exclusion Criteria

Subjects are ineligible to enroll in this study if they fulfill any of the following exclusion criteria.

- 1. Other malignancies treated within the last 5 years, except *in situ* cervix carcinoma or non-melanoma skin cancer.
- 2. Other form(s) of antineoplastic therapy anticipated during the period of the study.
- 3. Previous severe hypersensitivity reaction to another fully human monoclonal antibody or severe reaction to immuno-oncology agents, such as colitis or pneumonitis requiring treatment with steroids.

Confidential Page 29 of 78

- 4. History of interstitial lung disease.
- 5. Primary or secondary immunodeficiency, including immunosuppressive disease, autoimmune disease (including autoimmune endocrinopathies), or usage of immunosuppressive medications.

Note: Subjects with diabetes type 1, vitiligo, psoriasis, hypo-, or hyperthyroid disease not requiring immunosuppressive treatment are eligible. Subjects with Type 2 diabetes mellitus are allowed.

- 6. Subjects with a known history of human immunodeficiency virus 1 and 2, human T lymphotropic virus 1.
 - **Subjects in Phase 2 with HCC:** Subjects with active hepatitis B infection who are receiving effective antiviral therapy are permitted. Subjects with active hepatitis C infection are allowed (antiviral therapy not required).
- 7. Administration of anticancer medications or investigational drugs within the following intervals before the first administration of study drug:
 - a. ≤14 days for chemotherapy, targeted small molecule therapy, or radiation therapy. Subjects must also not have had radiation pneumonitis as a result of treatment and cannot participate in the study if they are on chronic corticosteroids for radiation pneumonitis. A 1-week washout is permitted for palliative radiation to non—central nervous system (CNS) disease, with medical monitor approval.

Note: Bisphosphonates and denosumab are permitted medications.

- b. ≤14 days for prior immunotherapy. Subjects in the dose escalation cohorts are excluded if they have received prior checkpoint inhibitors, costimulatory agonists, or immune modulating therapy except as described below. Once a dose level is determined to be safe by the SRC, subjects will be allowed to enroll in dose-level expansion cohorts if they have received other non–CTLA-4 targeting immunotherapies.
- c. Subjects enrolling in Phase 2 must have cancer that has progressed after prior treatment with an approved or investigational PD-1/PD-L1 inhibitor as their most recent therapy (2-6 weeks prior to first dose of study drug). The minimum requirement of 2 weeks (14 days) from prior anti−PD-1/PD-L1 therapy is to allow resolution of any lower-grade (≤2) adverse events observed with the therapy. If the investigator feels the subject has tolerated prior anti−PD-1/PD-L1 therapy well, then treatment with study agent may begin sooner.
- d. \leq 7 days for prior corticosteroid treatment, with the following exceptions:
 - Use of an inhaled or topical corticosteroid is permitted.
 - Corticosteroid premedication for radiographic imaging for dye allergies is permitted.
 - Use of physiologic corticosteroid replacement therapy may be approved after consultation with the medical monitor.

Confidential Page 30 of 78

- e. \leq 21 days for prior monoclonal antibody used for anticancer therapy, with the exception of denosumab. This does not apply to subjects being enrolled in Phase 2, who have received a PD-1/PD-L1 inhibitor as their most recent therapy (2-6 weeks prior to first dose of study drug; see above).
- f. \leq 7 days for immunosuppressive-based treatment for any reason, with the exceptions noted above for prior corticosteroid treatment (exclusion criterion d).
- g. \leq 21 days or 5 half-lives before first dose of study treatment for all other investigational study drugs or devices. For investigational agents with long half-lives (e.g., >5 days), enrollment before the fifth half-life requires medical monitor approval.
- h. For subjects in Phase 2 with HCC < 6 weeks for prior locoregional therapy to the liver e.g., transcatheter chemoembolization (TACE), radiation, surgery, or radioembolization.
- 8. Has not recovered to grade ≤1 from toxic effects of prior therapy and/or complications from prior surgical intervention before starting therapy.
 - **Note**: Subjects with grade ≤ 2 neuropathy and alopecia are an exception and may enroll.
- 9. Uncontrolled infection or other serious medical illnesses.
- 10. History or presence of an abnormal ECG that, in the investigator's opinion, is clinically meaningful.
- 11. Any medical conditions that, in the opinion of the investigator, would preclude use of AGEN1884, including AGEN1884 hypersensitivity.
- 12. Women who are pregnant or breastfeeding.
- 13. Concurrent participation in other investigational drug trials.
- 14. Has a CNS tumor, metastasis(es), and/or carcinomatous meningitis identified either on the baseline brain imaging obtained during the screening period or identified prior to consent.

Note: Subjects with history of brain metastases that have been treated may participate provided they show evidence of stable supra-tentorial lesions at screening (defined as 2 brain images, both of which are obtained after treatment to the brain metastases. These imaging scans should both be obtained ≥ 4 weeks apart). In addition, any neurologic symptoms that developed either as a result of the brain metastases or their treatment must have returned to baseline or resolved. For individuals who received steroids as part of brain metastases treatment, steroids must be discontinued ≥ 7 days prior to first dose of study drug.

15. For subjects in Phase 2 with HCC, the following exclusions also apply:

- a. Recent encephalopathy episodes in the last 6 months.
- b. Recent (within the last 3 months) gastro-esophageal varices bleeding.
- c. Subject whose tumors have cardiac involvement, as determined by imaging.

Confidential Page 31 of 78

3.3 Randomization

No randomization to treatment assignments will be performed in this study.

3.4 Blinding

The study will be open label; no blinding will be performed.

3.5 Discontinuation of Therapy

Treatment with AGEN1884 should be discontinued if 1 of the following primary reasons occur:

- Unacceptable toxicity (based on the investigator's clinical decision that the subject is unable to tolerate therapy).
- Adverse event
- Radiographic progression of disease (compared to baseline assessment). Disease progression is defined as progression confirmed by a second, consecutive assessment ≥6 weeks apart.

Note: If subject with evaluation of disease progression is having clinical benefit despite the progression, treatment may continue following discussion with, and approval of the medical monitor.

- Investigator decision
- Clinical progression of disease
- Protocol deviation
- Subject completed treatment
- Investigator decision
- Subject noncompliance with protocol for nonmedical reasons

Subjects who discontinue therapy prior to progression should continue to be followed for response and complete disease assessments every 12 weeks according to standard of care for up to 2 years from first AGEN1884 administration. Subjects will be followed for safety ≥90 days following the last administration of investigational agent, as described in Section 5.8.

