3.7 Treatment Beyond Disease Progression

Subjects will be permitted, with the Sponsor's approval, to continue with treatment beyond initial RECIST 1.1 defined PD as long as they meet the following criteria:

- Investigator-assessed clinical benefit from the treatment;
- Subject is clinically stable;
- Subject is tolerating study drug; and
- There is agreement with the sponsor.

The assessment of clinical benefit should take into account whether the subject is clinically deteriorating and unlikely to receive further benefit from continued treatment. The following criteria need to be taken into consideration:

- Absence of clinical symptoms and signs (including worsening of laboratory values) indicating disease progression.
- No decline in ECOG performance status.
- Absence of rapid progression of disease or of progressive tumor at critical anatomical sites (e.g., cord compression) requiring urgent alternative medical intervention.

Subjects should discontinue study therapy upon evidence of further progression, defined as an additional 10% or greater increase in tumor burden from time of initial progression (including all target lesions and new measurable lesions).

Imaging is required every 6 weeks (± 3 days) for those subjects with confirmed PD who remain on AGEN1884 until treatment is discontinued.

4. Investigational Agent

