4.1.1 Dosage and Administration

AGEN1884 will be administered intravenously (IV) for each cycle (3 weeks) as a 60-min (-10/+20 min) infusion. Infusions will be followed immediately by a 15-min saline flush of the IV line.

Treatment will be administered every 3 weeks for the first 4 cycles.

At the 12-week evaluation timepoint, subjects may continue to receive AGEN1884 every 3, 6, or 12 weeks (\pm 7 days) for a maximum duration of 1 year of treatment, provided they were not diagnosed with PD and were tolerating the study drug. The appropriate schedule will be based on discussion with the medical monitor. Subjects who progressed yet still have clinical benefit from treatment may continue on treatment following discussion with, and approval of, the medical monitor. For detailed criteria and consideration for treatment post-progression, refer to Section 3.7. Dosing is described in Table 1.

Please refer to the Pharmacy Manual for further instructions on AGEN1884 dosage and administration.

Confidential Page 33 of 78

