- Partial Response (PR): At least a 30% decrease in the sum of diameters of target lesions, taking as reference the baseline sum diameters.
- Progressive Disease (PD): At least a 20% increase in the sum of diameters of target lesions, taking as reference the smallest sum on study (this includes the baseline sum if that is the smallest on study). In addition to the relative increase of 20%, the sum must also demonstrate an absolute increase of at least 5 mm. (Note: the appearance of one or more new lesions is also considered progression).
- Stable Disease (SD): Neither sufficient shrinkage to qualify for PR nor sufficient increase to qualify for PD, taking as reference the smallest sum diameters while on study.

Evaluation of non-target lesions

- Complete Response (CR): Disappearance of all non-target lesions and normalization of tumor marker level. All lymph nodes must be non-pathological in size (<10mm short axis).
- Non-CR/Non-PD: Persistence of one or more non-target lesion(s) and/or maintenance of tumor marker level above the normal limits.
- Non-CR/Non-PD: Persistence of one or more non-target lesion(s) and/or maintenance of tumor marker level above the normal limits.
- Progressive Disease (PD): Unequivocal progression of existing non-target lesions. (Note: the appearance of one or more new lesions is also considered progression).

Confidential Page 76 of 78

Table 1 - Time point response: patients with target (+/-
non-target) disease.	

Target lesions	Non-target lesions	New lesions	Overall response
CR	CR	No	CR
CR	Non-CR/non-PD	No	PR
CR	Not evaluated	No	PR
PR	Non-PD or not all evaluated	No	PR
SD	Non-PD or not all evaluated	No	SD
Not all evaluated	Non-PD	No	NE
PD	Any	Yes or No	PD
Any	PD	Yes or No	PD
Any	Any	Yes	PD

CR = complete response, PR = partial response, SD = stable disease, PD = progressive disease, and NE = inevaluable.

Table 2 – Time point response: patients with non-target disease only.

Non-target lesions	New lesions	Overall response
CR	No	CR
Non-CR/non-PD	No	Non-CR/non-PDa
Not all evaluated	No	NE
Unequivocal PD	Yes or No	PD
Any	Yes	PD
CR = complete response NE = inevaluable.	, PD = progressive	e disease, and

a 'Non-CR/non-PD' is preferred over 'stable disease' for non-target disease since SD is increasingly used as endpoint for assessment of efficacy in some trials so to assign this category when no lesions can be measured is not advised.

Confidential Page 77 of 78

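### Protocol Sections 3.5, 3.7 and 4.1.1, Table 10 and Appendix E give different rules for when progression counts for stopping treatment, who approves continuation, and when the first two scans fall.

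*Protocol*

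**What the plan says.** **Protocol Section 3.5.** One listed reason for stopping is "Radiographic progression of disease (compared to baseline assessment"). The next sentence reads: "Disease progression is defined as progression confirmed by a second, consecutive assessment ≥6 weeks apart". A Note adds that, where a subject with progression is benefiting clinically, "treatment may continue following discussion with, and approval of the medical monitor". Clinical progression, investigator decision and adverse event are separate reasons to stop.

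**Protocol Section 3.7.** "Subjects will be permitted, with the Sponsor's approval, to continue with treatment beyond initial RECIST 1.1 defined PD", subject to clinical benefit, clinical stability, tolerance and sponsor agreement. Treatment then stops at further progression, "defined as an additional 10% or greater increase in tumor burden from time of initial progression". The six-weekly imaging in the same section is required for subjects whose PD is confirmed.

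**Protocol Section 4.1.1.** After the 12-week evaluation, dosing may go on "provided they were not diagnosed with PD and were tolerating the study drug". Subjects who progressed but still benefit may continue if the medical monitor approves, and the reader is sent to Section 3.7 for the criteria. Section 3.1 carries the same exception and bases the 12-week decision on two scans.

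**Table 10.** Footnote e limits dosing after Week 12 to subjects with SD, PR or CR and does not repeat the clinical-benefit exception. Footnote d, attached to the imaging row, sets the first two scans at Weeks 6 and 12; Sections 3.1 and 5.7.1 agree. The grid marks the imaging row under Week 7 (D1 C3, ±3 days) and Week 12 (D15 C4, ±2 days).

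**Appendix E.** PD in target lesions is an increase of at least 20% and 5 mm, "taking as reference the smallest sum on study". No confirming scan is required.

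**The concern.** A site with a first PD scan in hand has to answer three questions: is this progression for the purpose of stopping, is approval needed before the next dose, and from whom? The protocol answers each in more than one way. Two sites following it in good faith could act differently on identical scans, one seeking approval and applying the Section 3.7 checks at once, the other waiting for a confirming scan.

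The first stake is subject safety, because the Section 3.7 checks on stability, symptoms and performance status are the safeguard for treatment after progression. The second is the data. The SAP's primary analyses of best overall response, duration of response, disease control and PFS (Sections 8.7.1 to 8.7.3 and 8.7.6) look past a transient PD when later assessments support doing so. How many such assessments exist depends partly on who stays on treatment and is scanned after a first PD.

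**Working it through.** The plan gives no figure to reproduce. The check has three parts.

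**1. The rules side by side**

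| Place | Reference sum | Confirmation of PD | Who approves continuation |
|---|---|---|---|
| 3.5 | Baseline | Second consecutive scan, at least 6 weeks apart | Medical monitor |
| 3.7 | RECIST 1.1 (Appendix E) | Not needed: criteria run from initial PD | Sponsor |
| 4.1.1 | Not stated | Not mentioned | Medical monitor |
| Table 10, footnote e | Not stated | Not mentioned | No exception given |
| Appendix E | Smallest sum on study | None | Not applicable |

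Take a PD first seen at the Week 12 scan. It cannot yet be confirmed, so under 3.5 it is not disease progression. Under 4.1.1 it already prevents further dosing without approval, and under 3.7 the approval criteria already apply.

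**2. The reference sum**

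Illustration with assumed sums, applying the Appendix E 20% threshold to both references (3.5 states no percentage): baseline 100 mm, smallest sum 60 mm.

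- Appendix E: the larger of 60 × 1.2 = 72 and 60 + 5 = 65, so PD at 72 mm.
- Against baseline: 100 × 1.2 = 120 mm.
- Difference: 120 − 72 = 48 mm.

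The two agree while baseline is still the smallest sum, and the difference grows with the depth of earlier shrinkage. A new lesion is PD under Appendix E whatever the reference.

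**3. The interval between the first two scans, against 6 weeks = 42 days**

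Inputs: first dose on Day 1 and 21-day cycles. D1 C3 = 1 + 2 × 21 = Day 43. D1 C4 = 1 + 3 × 21 = Day 64. D15 C4 = 64 + 14 = Day 78.

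*Table 10 grid* (Day 43 ± 3, Day 78 ± 2):
- Nominal gap: 78 − 43 = 35 days.
- Shortest: 76 − 46 = 30 days. Longest: 80 − 40 = 40 days.
- Of the 7 × 5 = 35 in-window day pairs, none reaches 42.

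*Text schedule* (Weeks 6 and 12):
- Nominal gap: 6 weeks = 42 days, which just meets the rule.
- As calendar weeks (Days 36–42 and 78–84): 36 to 48 days; 28 of 49 day pairs reach 42.
- As Days 42 and 84 with the grid's windows (an assumption, since footnote d gives none): 37 to 47 days; 20 of 35 pairs reach 42.

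*Sensitivity.* If D15 C4 were counted from a fourth dose given 7 days late, the longest grid gap would be (64 + 7 + 14 + 2) − 40 = 47 days. Section 5.7.1, however, keeps scans on the original schedule when dosing is delayed.

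**The case against.** The strongest reply is that approval is required on every route. The 3.5 Note, 4.1.1 and 3.7 each ask for it before treatment continues past progression; 4.1.1 points to 3.7, so the two were meant to be read together; and 3.5 lets the investigator stop for clinical progression or on judgement. The medical monitor may also act for the Sponsor: Section 3.1.1 names the two together in the safety committee's membership. Finally, the efficacy endpoints use RECIST 1.1 progression, scan stopping is set in Section 5.7.1, and the SAP has a first-PD sensitivity analysis. None of these uses the 3.5 definition.

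Much of this stands and limits the practical effect. It does not settle when approval becomes necessary. Read with the sentence before it, the 3.5 Note takes effect at confirmed progression, whereas 3.7 takes effect at the first PD. Nor can Appendix E be set aside as serving response assessment only, since 3.7 rests a treatment decision on RECIST 1.1 PD.

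Stronger readings are tempting but not supported:

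- *The first two scans can never satisfy the 6-week rule.* This is true of the Table 10 grid with windows counted from Day 1. It is not true of the Week 6 and Week 12 schedule in footnote d and the text.
- *Section 4.1.1 forbids all dosing after PD.* It allows continuation for clinical benefit with approval.
- *Section 3.5 stops treatment only on confirmed progression.* Clinical progression, investigator decision and adverse event are separate grounds.
- *A subject with PD on both scans could be dosed until about Day 120.* The nominal next six-weekly scan is 78 + 42 = Day 120, but that is when the 3.5 definition might first be met, not exposure the protocol permits. The fourth dose is Day 64, and dosing after the 12-week evaluation requires no PD or an approval.

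**Conclusion.** The concern holds as a conflict between sections. A first PD scan can be not yet progression under 3.5 and at the same time trigger the approval requirement under 3.7 and 4.1.1. The reference sum and the named approver also differ. The 3.5 Note and the clinical-benefit sentence in 4.1.1 narrow the conflict without removing it.

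Separately, Table 10 contradicts its own footnote d on the first scan. The grid gap of 35 days (30 to 40) cannot meet a 6-week interval; the text schedule meets it at 42 days with no margin. The grid result assumes 21-day cycles, windows counted from Day 1 and scans kept on the original schedule.

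The consequence most exposed is the dosing between a first PD at the Week 6 or 7 scan and the 12-week evaluation, where 3.5 read alone asks for nothing and 3.7 asks for approval. How many subjects this affects, and how far it changes the post-PD scans available to the SAP, cannot be derived from the documents.

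**What to change.** Reconcile Protocol Sections 3.5, 3.7 and 4.1.1, Table 10 (grid and footnotes d and e) and Appendix E, so that each of these is stated once and used consistently:

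- the reference sum for progression in the stopping decision;
- whether confirmation is needed;
- the point at which approval to continue is required;
- who gives that approval;
- the timing of the first two scans, with their windows.

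The sponsor's clinical lead decides the rule; no particular rule or interval is proposed here. The cost is protocol wording, with the ethics approval that Section 7.1 requires for a protocol change. No sample size or analysis method changes.
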